underlying disease or condition under investigation or other events that commonly occur in the study population independent of drug therapy) that indicates those events occur more frequently in the drug treatment group than in a concurrent or historical control group.

- *Findings from other studies.* Investigators will report any findings from epidemiological studies, pooled analysis of multiple studies, or clinical studies whether or not conducted under an IND, and whether or not conducted by the sponsor, that suggest a significant risk in humans exposed to the drug. Ordinarily, such a finding would result in a safety-related change in the protocol, informed consent, investigator brochure (excluding routine updates of these documents), or other aspects of the overall conduct of the clinical investigation.
- *Findings from animal or in vitro testing.* Investigators will report any findings from animal or in vitro testing, that suggest a significant risk in humans exposed to the drug, such as reports of mutagenicity, teratogenicity, or carcinogenicity, or reports of significant organ toxicity at or near the expected human exposure. Ordinarily, any such findings would result in a safety-related change in the protocol, informed consent, investigator brochure (excluding routine updates of these documents), or other aspects of the overall conduct of the clinical investigation.
- *Increased rate of occurrence of serious suspected adverse reactions.* Investigators will report any clinically important increase in the rate of a serious suspected adverse reaction over that listed in the protocol or investigator brochure.
- *Submission of IND safety reports.* Investigators will annually submit each IND safety report in a narrative format or on FDA Form 3500A or in an electronic format that FDA can process, review, and archive. Each notification to FDA will be transmitted to the review division in the Center for Drug Evaluation and Research or in the Center for Biologics Evaluation and Research that has responsibility for review of the IND. Upon request from FDA, the investigators will submit to FDA any additional data or information that the agency deems necessary, as soon as possible, but in no case later than 15 calendar days after receiving the request.
- *Unexpected fatal or life-threatening suspected adverse reaction reports.* Investigators will notify FDA of any unexpected fatal or life-threatening suspected adverse reaction as soon as possible but in no case later than 7 calendar days after the sponsor's initial receipt of the information.

Study Registration

The research program including the clinical trial will be registered at ClinicalTrials.gov.

Risks and Benefits of Participating in this Research Program

Possible Benefits:

It is possible that patients will have improvements in their PTH patterns following treatment with erenumab.

Possible Risks:

Erenumab has been shown to be well tolerated and associated with few side effects. The most common side effects are injection site reaction, constipation, muscle spasm, and pruritis. With the exception of injection site reaction (5.2%), these side effects were reported by less than 5% of patients in the phase II and III clinical trials of migraine. Constipation, sometimes with serious complications, was reported by approximately 3% of individuals receiving erenumab.

Development of hypertension and worsening of pre-existing hypertension have been reported following the use of erenumab in the postmarketing setting. Many of the patients had pre-existing hypertension or risk factors for hypertension. There were cases requiring pharmacological treatment and, in some cases, hospitalization. Hypertension may occur at any time during treatment but was most frequently reported within seven days of dose administration. In the majority of cases, the onset or worsening of hypertension was reported after the first dose.

The FDA has added a safety-related label change to erenumab to include a contraindication for patients with serious hypersensitivity to erenumab or to any of the excipients due to the risk of anaphylaxis and angioedema. Most hypersensitivity reactions were not serious and occurred within hours of administration, although some occurred more than one week after administration.

Additional risks that have been reported since erenumab was approved in May 2018 include mouth/lip sores and skin and subcutaneous tissue disorders such as alopecia and rash.

Potential risks associated with erenumab use during pregnancy and lactation are not established.

Protected health information (PHI) is being collected. Although measures are taken to reduce the risk, it is possible that there could be inappropriate access to the PHI by individuals not approved for such access.

There is a possibility that the stress and stimulation of participating in the research study could transiently exacerbate one's headache.

A research participant that indicates suicidal or homicidal intent on a study questionnaire will be referred to the Emergency Department for evaluation.

Protection Against Risks:

Individuals who are known to be pregnant or breastfeeding will be excluded from study participation.

Women of childbearing potential who are not known to be pregnant will have pregnancy testing at the baseline visit and prior to each treatment with study drug. Women found to be pregnant prior to treatment will not receive treatment. Women found to be pregnant after the initial treatment will not receive further study drug. Women of childbearing potential will be required to use a reliable form of contraception from the time of study enrollment through 16 weeks after the dose of erenumab.

Measures that will be taken to protect PHI: All information collected from study participants will be locked in a secure location. Identifying information will be removed from the data forms and replaced by unidentifiable codes. Electronic databases/spreadsheets will be password protected and only accessible to those with access rights.

Patient Retention

Subject retention and diary compliance will be essential for study success.

At the time of considering an individual for participation in this study, it will be ensured that the individual will be available for the duration of the study. The responsibilities of the subject will be clearly defined. Subjects will be contacted with reminders prior to each research appointment.

Diary compliance will be monitored on an ongoing basis. Subjects will be contacted immediately if non-compliance is observed.

Protocol Maintenance

Protocol modifications will be approved by the principal investigator and submitted to the IRB in accordance with IRB rules and regulations. Modifications will be documented separately and within the main protocol document with a newly assigned date and version number.

ISS – Timeframes for Submission of Safety Data to Amgen

For Interventional studies with Amgen IMP*:

Safety Data	Timeframe for Submission to Amgen
Suspected Unexpected Serious Adverse Reaction (SUSARs)	Sent to Amgen at time of regulatory submission
Serious Adverse Events (SAEs)	Not required, unless contractually specified per study
Adverse Events not meeting serious criteria	Not required, unless contractually specified per study

Events of Interest	Not required, unless contractually specified per study
Pregnancy/Lactation	Within 10 calendar days of Sponsor awareness
Event listing for reconciliation	As specified per contract

*Specific requirements are to be outlined in the Research Agreement

For all studies – aggregate reports*:

Safety Data	Timeframe for submission to Amgen
Annual Safety Report (eg, EU Clinical Trial Directive [CTD] DSUR , and US IND Annual Report)	Annually
Other Aggregate Analyses (any report containing safety data generated during the course of a study)	At time of ISS sponsor submission to any body governing research conduct (eg, RA, IRB, etc)
Final (End of Study Report, including): 
• Unblinding data for blinded studies• Reports of unauthorized use of a marketed product	At time of ISS sponsor submission to any body governing research conduct (eg, RA, IRB, etc) but not later than 1 calendar year of study completion

*Specific requirements are to be outlined in the Research Agreement

Data Sharing

FITBIR (Federal Interagency Traumatic Brain Injury (FITBIR) informatics system):
FITBIR is a computer system run by the National Institutes of Health that allows researchers to share information with each other. Data from this study will be submitted to FITBIR. Before data are submitted, PHI will be replaced with a code number. Subjects will have the ability to opt out from having their data shared to FITBIR.

References

1. Headache Classification Committee of the International Headache Society (IHS) The International Classification of Headache Disorders, 3rd edition. *Cephalgia* 2018;38:1-211.

4. Erickson JC. Treatment outcomes of chronic post-traumatic headaches after mild head trauma in us soldiers: An observational study. *Headache* 2011;51:932-44.

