e)	Imaging evidence of traumatic head injury
2.	Associated, immediately following the head injury, with at least one:
a)	Transient confusion, disorientation or impaired consciousness
b)	Loss of memory for events immediately before or after injury
c)	Two or more of: nausea, vomiting, visual disturbance, dizziness/vertigo, impaired memory/concentration, gait instability
C.	Headache is reported to have developed within 7 days after one of:
1.	The injury to the head
2.	Regaining consciousness following injury to the head
3.	Discontinuation of medication(s) that impair the ability to sense or report headache following injury to the head
D.	If headache persists for >3 months following onset then it is "persistent" PTH. If headache resolved within 3 months of onset or 3 months have not yet passed, then it is "acute" PTH.
E.	Not better accounted for by another ICHD-3 diagnosis

- PTH onset 7- 56 days prior to the time of enrollment
- Adults 18-70 years of age
- Willing to receive erenumab treatment
- Willing to maintain a headache diary
- Willing and able to return for follow-up visits

Additional Inclusion Criteria for the Clinical Trial (assessed after run-in phase)

- 4 or more moderate or severe headache days during the 4-week run-in phase

- An increase of at least 2 moderate to severe headache days compared to pre-TBI
- At least a 30% increase in moderate to severe headache days compared to pre-TBI
- At least 80% compliant with diary keeping during the 4-week run-in phase (i.e. provides data on at least 80% of days)

Exclusion Criteria

- Chronic headache (i.e. at least 15 headache days/month for more than 3 months) within 12 months prior to the mTBI that led to the current PTH, including PPTH, chronic migraine, medication overuse headache, new daily persistent headache, hemicrania continua, chronic tension-type headache.
- Diminished decision-making capacity that in the investigator's opinion would interfere with the person's ability to provide informed consent and complete study procedures
- Started or changed dose of a headache preventive medication within the 3 months prior to screening.
- Use of onabotulinumtoxinA in the head, neck or face region within 6 months of screening
- During the 6 months before screening, use of opioids or barbiturates on an average of at least 4 days per month

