
during the open label extension were similar to that observed in the double-blind phase and comparable to placebo.

Hypothesis/Objective

The objective of this study is to collect hypothesis generating data about whether intervention with erenumab is an effective treatment for PTH attributed to mTBI. Participants will receive erenumab when PTH has been present for 35-84 days. Once PTH has been persistent for this period of time, patients may be less likely to remit or improve spontaneously compared to if they were enrolled earlier after PTH onset. Thus, this population of individuals with PTH would be considered in high need of treatment.

Specific Aims/Study Endpoints

Primary endpoint

- Moderate-to-severe headache day frequency measured at weeks 9-12 after administration of first dose of erenumab 140mg vs. frequency of moderate-to-severe headache days during the 4-week baseline phase (BP). A moderate-to-severe headache day is defined as any headache lasting at least 2 hours and which at any point reaches at least moderate intensity.

Secondary endpoints

- Percentage of patients with at least a 50% reduction in headache days during weeks 9-12 after administration of first dose of erenumab 140 mg compared to BP.
- Percentage of patients with chronic headache defined as ≥ 15 headache days during weeks 9-12 after administration of first dose of erenumab 140mg compared to BP.
- Headache Impact Test (HIT-6) at weeks 9-12 after administration of first dose of erenumab 140 mg compared to BP.
- Acute treatment day frequency measured at weeks 9-12 after administration of first dose of erenumab 140mg compared to BP. (Acute treatment day is any day on which an analgesic, triptan, or ergotamine containing medication is taken, or device neuromodulation [e.g. vagal or trigeminal nerve electrical stimulation or single pulse transcranial magnetic stimulation] is administered to relieve headache)

Methods

This is a phase II prospective, open-label clinical trial of a CGRP receptor mAb for treatment of PTH. Of note, this was originally designed as a randomized, placebo-controlled clinical trial. However, recruitment into the clinical trial was slow. Since the estimated total enrollment would

be inadequate for making comparisons between the placebo and erenumab groups, the study was revised to an open-label design.

[figure not shown]

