Individuals with PTH will be receive monthly subcutaneous administration of erenumab 140 mg over a 3-month period (total of 3 injections). The primary endpoint will be the mean number of moderate-to-severe headache days between 9-12 weeks after treatment vs. the number of moderate-to-severe headache days during the 4-week BP. Subjects will maintain an electronic daily diary during the 4-week BP, for the 12 weeks post-first treatment, and during weeks 21-24 post-first treatment.

All participants in this clinical trial will complete baseline and follow-up questionnaires described in detail in the separate human studies protocol subtitled "Individual Projects Excluding Clinical Trial" within the "Phenotyping and Neurophysiology" section. In brief, the following questionnaires will be used to collect baseline and follow-up data:

- 1) TBI and PTH characteristics
- 2) Post-TBI symptoms using the 22-item Symptom Evaluation Checklist from the Sport Concussion Assessment Tool (SCAT)
- 3) Headache Impact Test (HIT-6)
- 4) Self-Rating Questionnaire on Hypersensitivity to Sound
- 5) Photosensitivity Assessment Questionnaire
- 6) Allodynia Symptom Checklist (ASC-12)
- 7) State Trait Anxiety Inventory (STAI)
- 8) Beck Depression Inventory (BDI)
- 9) Posttraumatic Stress Disorder Checklist
- 10) Survey of Autonomic Symptoms
- 11) Pain Catastrophizing Questionnaire
- 12) Insomnia Severity Index
- 13) Cognitive Function
- 14) Dizziness Handicap Inventory
- 15) Trail Making Test A and B
- 16) Controlled Oral Word Association Test (COWAT)
- 17) Global Impression of Change
- 18) Follow-up Headache Characteristics
- 19) Adverse Events
- 20) Sensory Testing Results *not applicable for Rochester and Florida sites
- 21) Vital Signs
- 22) Pregnancy Test Results

In addition, all research participants will maintain a daily electronic headache and symptom diary to provide data on headaches, treatment, and presence and severity of associated symptoms. The diary will be maintained for the first 4 weeks, starting with enrollment (i.e. first research visit) and through week 16 (i.e. third research visit), and again during weeks 21-24 post-first treatment. The electronic diary requires individuals to record whether they did or did not have a headache each day, the severity of their pain, headache duration, level of functional disability due to the headache, and use of medication. To optimize compliance with diary maintenance, the amount of

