time required to complete the daily entries has been minimized to less than 2 minutes. Subjects are asked to complete their headache diary at the end of each day. Data from the headache and symptom diary will be used to assess changes in symptoms over time, to prospectively determine who has persistence vs. resolution of PTH, to determine enrollment in the clinical trial depending on PTH persistence and frequency of moderate to severe headache days, and to track response to treatment for those individuals enrolled into the clinical trial.

Stratification, Randomization and Masking: This is an open-label study in which there is no stratification, randomization, or masking.

All study drugs will be prepared by a Mayo Clinic pharmacist who has no other role in the study. The drug will be delivered by pharmacy staff to the enrolling investigator clinician or research nurse, who will be responsible for delivering the injection. There will be strict adherence to inclusion and exclusion criteria. Participants will receive instructions and training from a study coordinator on how to use the electronic diary for daily reporting of headaches. A urine pregnancy test will be required for female participants prior to each of the erenumab treatments. Throughout the study, participants will record data in the daily diary for the previous 24 h period.

Treatment with Erenumab: Patients receive treatment with 140 mg of erenumab via subcutaneous injection. Treatment will be administered under research team observation. Injections will be administered using two 70 mg/1 mL prefilled syringes in the abdomen (except for a two-inch area right around the navel), thigh, or outer area of upper arm according to patient preference. If using the same body site for the two separate injections, the second injection is not to be given at the same spot used for the first injection.

Erenumab will be stored refrigerated at 2°C to 8°C (36°F to 46°F) until time of use. Once removed from the refrigerator, it will be kept at room temperature and used within 7 days. Prior to administration, erenumab will sit at room temperature for at least 30 minutes, protected from direct sunlight.

Concomitant Therapy

There are no restrictions on the use of as needed headache/pain therapies. Patients will record their use of such therapies within the headache diary and these data will be used when measuring patient outcomes.

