For patients who are participating in the clinical trial, no preventive therapy for headache should be started. Preventive therapies include drugs, biologics, devices, procedures, and non-pharmacological modalities.

Statistical Plan:

Sample Size- all individuals who qualify for the clinical trial and are interested in participating will be enrolled, up to a maximum of 112 participants. This sample size is empirical and results will be used for hypothesis generation.

Headache Diary - Values for missing calendar day entries in a given month will be imputed by prorating scores of 4-week post-treatment periods with 20–27 days of diary data. For months with less than 10 days of diary data, scores will be estimated by the substitution of the patient's previous 28-day period mean score, multiplied by the ratio of the mean for all patients in the same period and divided by the mean for all patients in the previous period. For post-treatment periods with 10–19 days of diary data, scores were estimated using a mean of both methods.

Outcomes - Efficacy analyses will be conducted in the full analysis set, which includes all subjects (intent-to-treat population) who received at least one dose of study drug and have at least 10 days of efficacy assessments for the primary endpoint measured during weeks 9–12. Safety analyses will be performed in all subjects who receive at least one dose of study drug. The primary and secondary endpoints will be analyzed using a within-person one-sample t-test. Signed rank test will be used for the primary analysis if there is a deviation from normality assumption as assessed by Shapiro Wilk's test. Confidence intervals will be calculated. SAS version 9.4 (SAS Institute, Cary NC) will be used for all statistical analyses.

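### The on-study rule bars starting a headache preventive but, in the text available, not changing its dose or stopping it, although eligibility treats a dose change as disqualifying; the likely effect is small

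*Combined protocol and SAP*

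**What the plan says.** The Exclusion Criteria for Path A/D and for Path C carry the same item: "Started or changed dose of a headache preventive medication within the 3 months prior to screening". It names two separate events and looks back from screening. It does not exclude someone whose preventive has been stable.

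The rule after entry is in Concomitant Therapy: "For patients who are participating in the clinical trial, no preventive therapy for headache should be started". The next sentence sets its scope: "Preventive therapies include drugs, biologics, devices, procedures, and non-pharmacological modalities". As-needed treatment is left open: "There are no restrictions on the use of as needed headache/pain therapies".

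The additional trial criteria applied after the run-in begin with "4 or more moderate or severe headache days during the 4-week run-in phase" and continue with worsening relative to before the injury and diary compliance. None concerns preventives.

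The primary endpoint sets each patient's headache-day count in weeks 9-12 against the count in the four-week baseline. The study is open-label with no comparator. The Statistical Plan specifies a within-person one-sample t-test, or a signed rank test if normality fails, and says nothing about changes in background prevention. On sample size it states: "This sample size is empirical and results will be used for hypothesis generation".

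**The concern.** The eligibility item shows that the sponsor regards a dose change, like a start, as enough to disturb a stable background. The on-study rule carries over only the start. Its broad list of therapies suggests that stable prevention was the aim, so the omission reads as a drafting gap.

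With no control arm, nothing absorbs a change in background treatment. If a preventive is altered between baseline and weeks 9-12, its effect is counted with the change attributed to erenumab. An increase would tend to enlarge the apparent improvement, and a reduction or stop would tend to hide it. Both are plausible. Trial entry requires headache to be worse than before the injury, which is a reason to raise a dose. The Background section says that commonly used drugs may be poorly tolerated after concussion, which is a reason to lower or stop one.

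The plan also asks for no count of such changes, so a reader of the results could not tell whether any occurred.

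**Working it through.** **Reading the text.** The question is whether "For patients who are participating in the clinical trial, no preventive therapy for headache should be started" already covers dose changes.

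- If starting a therapy included changing its dose, the second half of "Started or changed dose of a headache preventive medication within the 3 months prior to screening" would be redundant. The protocol's own wording separates the two.
- The sentence "Preventive therapies include drugs, biologics, devices, procedures, and non-pharmacological modalities" widens which therapies count. It does not widen which actions are barred.
- The criteria assessed after the run-in do not test preventive stability.

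**Which periods are uncovered.** Headache onset is 7-56 days before enrollment, and the baseline diary is the first 28 days from enrollment. So 7 + 28 = 35 and 56 + 28 = 84, which reproduces the stated 35-84 days of headache at first dose. The treatment weeks clearly fall after the look-back. The baseline does too if screening precedes the run-in, which the contraception criterion suggests but which is not stated.

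**Who could be affected.** Headache must begin within 7 days of the injury (or of regaining consciousness or stopping a masking drug), so the injury is usually at most 56 + 7 = 63 days before enrollment. Three months is about 91 days, and 91 - 63 = 28. If screening is close to enrollment, a permitted preventive must usually have been unchanged since at least about 28 days before the injury. The group is narrow.

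**Illustrative size.** The documents give none of these inputs; all are assumptions:

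- share entering on a preventive: 10-20%
- share of those who change it: 10-30%
- effect of one change on weeks 9-12: 2 headache days
- SD of the within-person change: 4-7 days

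Share of patients with a change, g: 0.10 × 0.10 = 0.01 to 0.20 × 0.30 = 0.06. At n = 112 that is 1.1 to 6.7 patients.

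Shift in the mean = g × 2 × (2p - 1), where p is the share of changes in one direction:

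| p | Shift (days) |
|---|---|
| 1 (all one way) | 0.02 to 0.12 |
| 0.75 | 0.01 to 0.06 |
| 0.5 (balanced) | 0 |

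**Against precision.** The 95% half-width is t × SD/√n. At n = 112 (t = 1.98):

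| SD | Half-width (days) | 0.12 as a share of it |
|---|---|---|
| 4 | 0.75 | 16% |
| 5 | 0.94 | 13% |
| 6 | 1.12 | 11% |
| 7 | 1.31 | 9% |

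The 112 is a ceiling. At an assumed n = 50 the half-width is about 1.14 to 1.99 days, so 0.12 is about 6-11% of it, and the affected patients number 0.01 × 50 = 0.5 to 0.06 × 50 = 3.

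**Break-even.** To shift the mean by one half-width in the most precise case (0.75 days), g would have to be 0.75 / 2 = 37.5% of all patients, all changing in the same direction.

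**The case against.** The strongest case against the point is that it makes no practical difference. Every input to the size is assumed. The 0.12 is the top of one scenario, not a bound in any wider sense. A change early in the run-in could affect both periods, so charging the full 2 days to the contrast overstates it. Results are declared hypothesis-generating, as-needed therapy is unrestricted, and natural recovery and regression to the mean act on the same contrast and are not touched by this fix. All of this stands, and it limits the point to a minor one.

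The run-in half is also less certain than the treatment half. Screening is not defined in the text available. If eligibility is confirmed again after the run-in, a dose change there might fall within the three-month look-back. This is an ambiguity and not a rebuttal.

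The text available lacks the Participating Site Responsibilities section, and the companion protocol for the other individual projects was not available. Either could hold a stability rule.

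Finally, a restriction from the run-in onward would bind people who never receive erenumab, since about half are expected not to qualify. The plan already places trial conditions on everyone in the run-in, such as contraception and willingness to receive erenumab. That answers most of this objection, provided the limit ends for those who do not enter the trial.

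**Conclusion.** The gap is real but minor. In the text available, a dose change or a stop of an existing preventive during the treatment weeks, and probably during the run-in, breaches no stated rule. The size cannot be estimated from the documents. The 0 to 0.12 days in either direction rests wholly on the assumed shares, effect and SD, and it is small against the confidence interval throughout the range examined.

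A reader might infer more than this. One inference is that the protocol approves such changes; it is only silent, and its intent appears to be the opposite. Another is that the result will be biased in favor of erenumab; the direction is not fixed, and nothing in the documents says how many patients take a preventive or would alter it. A third is that the primary conclusion is unsafe for this reason; the stated purpose is hypothesis generation, and a shift of this order would be unlikely to alter it. The documents support none of the three. What they support is an inexpensive repair of one avoidable source of pre-post change.

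**What to change.** Reword the rule in Concomitant Therapy along these lines: from the start of the run-in through week 12, a headache preventive should not be started, stopped, or changed in dose or regimen, except for safety; the limit ends after the run-in for anyone who does not qualify for or does not enter the trial. Stopping must be named, or the same gap remains. Regimen is needed because dose does not fit devices, procedures and non-drug treatments. Naming the run-in also settles whether the bar on starting applies there.

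Record any change with its date as a deviation. Add no eligibility criterion, and keep the full analysis set primary. Report the number of patients with a change. A sensitivity analysis without them is optional: with perhaps 1-7 of 112 removed it would add little to the count, and excluding on post-dose changes can select better responders.

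The cost is one sentence, one reported count and a little extra recording. The diary captures "level of functional disability due to the headache, and use of medication", but the text available asks for no dates of preventive changes. Clinicians lose some freedom to adjust preventives for about 16 weeks (4 + 12), or 4 weeks in patients who later do not qualify. No one is excluded by the change, which matters because "recruitment into the clinical trial was slow". Some effect on willingness to consent or to stay cannot be ruled out, though the safety exception softens it.
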